4.2 Subject Demographics and Other Baseline Characteristics

4.2.1 Demographic Characteristics

Descriptive statistics [number of subjects (n), mean, standard deviation (SD), median, minimum and maximum values] for continuous variables and frequency count (n) and percentages (%) for all categorical variables will be presented.

The continuous variable includes age (in years) and categorical variables include sex, race and ethnicity. This data will be summarized descriptively for all subjects in Safety (Table 14.1.4.1) and ITT (Table 14.1.4.2) population by overall and will be listed (Listing 16.2.4.1).

Number and percentage of subjects in individual Kapur-Olshan retention and stability index sum score and group (Low and High) will be presented for all subjects in Safety (Table 14.1.4.1) and ITT (Table 14.1.4.2) population by overall. The listing of evaluation of well fit denture will be provided (Listing 16.2.4.2).

The current denture age (years) will be summarized descriptively for all subjects in Safety (Table 14.1.4.1) and ITT (Table 14.1.4.2) population by overall and complete denture history will be listed (Listing 16.2.4.3).

No formal statistical analysis will be performed for this data.

4.2.2 General Medical History

Medical history and current medical conditions will be listed in Listing 16.2.4.4, with start date and end date or ongoing.

4.3 Treatments (Study Product, Rescue Medication, other Concomitant Therapies, Compliance)

4.3.1 Study Product Compliance and Exposure

In this study single, common adhesive Super Poligrip Free will be used. 1.6g adhesive per treatment will be applied to each subject's dentures. This dose will be split as 1.00 ± 0.05 g for maxillary and 0.60 ± 0.05 g for mandibular dentures in accordance with consumer's normal distribution of adhesive.

The weight of adhesive applied to the dentures will be summarized descriptively (n, mean, SD, median, minimum and maximum) by treatment group and for lower, upper and combined

dentures (Table 14.2.1) on all subjects in ITT population. In the combined dentures the sum of weight of adhesive applied to lower and upper dentures will be obtained. The study product compliance data will be listed in Listing 16.2.5.1 on all randomized subjects.

4.3.2 Prior and Concomitant Medication

Prior or concomitant medication taken by or administered to a subject will be recorded in the case report form. The prior and concomitant medications will be coded using an internal validated medication dictionary, GSKDrug.

Prior medications are defined as the medications started and stopped before first administration of study treatment (dentures were inserted). If the stop date is unknown or incomplete and medication cannot be considered as stopped prior to first administration of study treatment then the medication will be considered as concomitant medication.

Concomitant medications are defined as the medication started before the first administration of study treatment (dentures were inserted) and continued in the study or medication taken between the date of first dose and last dose of study treatment.

In this crossover study, the concomitant medication will be assigned to the treatment group based on the treatment being received at that date. Medication with date and time between the periods will be assigned to the treatment received in the previous period. Medications with a date after last treatment or the end of the study will be assigned to the treatment taken in the last period. In case the medication is taken during washout period, then it will be assigned to the most recent treatment period prior to washout.

Unknown dates will not be imputed, however if the start date is unknown, then it will be assumed to concomitant medication for all periods, unless the partial start date or stop date indicates differently.

Prior and concomitant medications/non-drug therapies will be listed by subject, with preferred term, indication, dose, dose form, frequency, route, start date, end date or ongoing and start day relative to first dose of study drug (Listing 16.2.5.2 and Listing 16.2.5.3).

4.4 Analysis of Efficacy

4.4.1 Primary Endpoint

4.4.1.1 Primary Endpoint Definition

The primary endpoint is defined as the combined mass of peanuts under maxillary and mandibular dentures.

4.4.1.2 Statistical Hypothesis, Model, and Method of Analysis

Food occlusion will be measured by weight of peanut particles (mass of retrieved peanuts in grams). Analysis will be performed on combined values (maxillary and mandibular dentures) of food occlusion.

Descriptive statistics (number of subjects, number of missing data, raw means, SD, standard errors [SE], median, minimum and maximum values) of combined masses of peanuts recovered from mandibular and maxillary dentures and their associated gauzes will be provided by treatment group (Table 14.2.2.1) for all subjects in ITT population.

The bar chart to display mean (\pm SE) of mass of peanuts recovered in each treatment group from mandibular (Figure 14.2.2), maxillary (Figure 14.2.3) and combined (Figure 14.2.1) dentures will be presented.

No formal statistical analysis as a primary analysis will be performed on this endpoint.

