1.2 Background and Rationale

The aim of this method development study is to assess if the changes made to the operational procedures from study 205915 result in an improved successful differentiation between the use of a denture adhesive and no denture adhesive in a model of food occlusion.

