1.2.1 Study Design Rationale

Based on previous findings, the peanut occlusion methodology has demonstrated the ability to detect differences in the mass of peanut particulate measured, and this protocol will continue to use the adhesive dissolution and peanut retrieval steps utilised in GSK studies CCI [REDACTED]

Whilst the objective measure of peanut mass is the primary endpoint of interest in this study, subject derived opinion of efficacy will also be measured by means of a subject-completed questionnaire. The number of denture dislodgements reported by the subjects during the chewing of the peanuts will also be collected and analysed and this, and the questionnaire data, will be used to support the findings of the peanut mass measure.

 GlaxoSmithKline	Document Name	208397 Clinical Protocol 2.docx		
	Type	Version	Document Identifier	Effective Date
	eldo_controlled	2.0; Most Recent; Effective; CURRENT	090032d580db1b91	24-Oct-2017 08:49:05
	Reason For Issue	Auto Issue		

Sodium-calcium mixed partial salt of poly(methylvinylether/maleic acid) and carboxymethylcellulose

208397

Final Clinical Protocol, 20 Oct 2017

Dentures are unique to each individual. Therefore, the most efficient approach to evaluating their performance with different adhesives or 'no adhesive' is a within subject comparison (i.e. a crossover design). Denture adhesive is used to secure dentures in the mouth. It forms a barrier that prevents food from entering the area between dentures and the edentulous ridge. This study will assess the objective measure of food occlusion while chewing peanuts as measured by mass of peanuts retrieved, as well as subjective measures of efficacy as measured by questionnaire data.

Peanuts were chosen as the model food in this methodology because they are a brittle food that, when masticated, break into small particles that can be recovered. Peanuts have therefore been retained as a model food for this study and to allow comparison with previous data.

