1.1 Study Design

This study is a single centre, controlled, open label, randomized, three-treatment, three-period, cross-over design in subjects with full upper and full lower dentures. Each treatment period will consist of one day of testing with at least two days between adjacent treatment visits.

All the study procedures (as defined in protocol) will be repeated in a crossover manner. There will be 2-30 days between treatment visits to allow for recovery from the mastication procedures.

At the screening visit, following an Oral Soft Tissue (OST) examination, each subject's dentures (upper and lower) will be cleaned then assessed for retention and stability using the Kapur Index (Olshan Modification) and whether they are well made. Only those subjects with dentures (both upper and lower) that satisfy both of these criteria will undergo the food migration adequacy assessment to provide evidence of adequate peanut particle migration under the dentures after chewing a portion of peanuts. A visual observation and rating of location and extent of peanut particle migration adequacy must indicate > 0 on a 0 - 3 scale. Subjects meeting all the inclusion criteria with no exclusions will then be randomised at Visit 2.

On each test day (Visits 2-4) subjects will undergo an OST examination and have their dentures cleaned. Treatment (or no treatment as per the randomization schedule) will then be applied as per the application instructions and the dentures worn by the subject. Then, 60 ± 5 minutes after inserting their dentures each subject will be given a standardized portion of

peanuts to consume, following a prescribed chewing and swallowing method. Whilst chewing the peanuts subjects will record the number of denture dislodgements that occur during the chewing procedure. After this, subjects will rinse their mouth with water. The examiner will then remove the lower denture and any peanut particles or adhesive remaining on the mandibular ridge will be removed using gauze. The examiner will then remove the upper denture and any peanut particles or adhesive remaining on the palate will be removed using new gauze. The subject will then complete a questionnaire on efficacy and a further OST examination will be performed.

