4.6 Additional Analysis

Adjusted means for mass of peanuts recovered from mandibular, maxillary (Table 16.1.9.2.1) and combined (Table 16.1.9.1.1) dentures, along with 95% confidence interval (CI) will also be reported by treatment group. These will be derived from a mixed model with period and treatment as fixed effects and subject as a random effect. The pair-wise comparisons will be performed and corresponding treatment differences, SE and 95% CI will be presented for all patients in ITT population. No p-value will be reported.

Using the same model as above, a subgroup analysis will be also conducted in low and high Kapur-Olshan groups of subjects. Adjusted means of combined masses of peanuts recovered from mandibular and maxillary denture, along with 95% CI will be presented by treatment groups for each sub-group (Table 16.1.9.3.1) for all patients in ITT population.

These results will be reported in the statistical appendix as part of CSR.

The assumptions underlying the mixed model will be examined using appropriate statistical method and if necessary, a suitable transformation of data or alternative non-parametric method based on ranks will be applied to obtain the inferential statistics. Hodges-Lehmann estimates of median of differences and Hodges-Lehmann 95% confidence intervals will be calculated.

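### Primary table and bar charts show raw per-treatment SEs unsuited to comparing treatments in a crossover; for mass this is presentation only, but dislodgements have no planned within-subject contrast

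*SAP*

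**What the plan says.** **Design and aim.** Protocol 1.2.1 reasons that, because every denture is individual, "the most efficient approach to evaluating their performance with different adhesives or 'no adhesive' is a within subject comparison". Protocol 1.2 asks whether the changed procedures "result in an improved successful differentiation between the use of a denture adhesive and no denture adhesive".

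**Primary output.** For combined mass, SAP 4.4.1.2 lists "raw means, SD, standard errors [SE], median, minimum and maximum values" by treatment group (Table 14.2.2.1). It then plans mean ± SE bar charts: "mass of peanuts recovered in each treatment group from mandibular (Figure 14.2.2), maxillary (Figure 14.2.3) and combined (Figure 14.2.1) dentures will be presented". The Table 14.2.2.1 shell has three treatment columns and no difference between them. The same section says that no formal analysis is done as the primary analysis.

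**Within-subject comparison of mass.** SAP 4.6 fits a mixed model with period and treatment as fixed effects and subject as a random effect. It reports pairwise differences, SEs and 95% CIs without p-values. Table 16.1.9.1.1 covers combined mass, Table 16.1.9.2.1 maxillary and mandibular mass, and Table 16.1.9.3.1 the Kapur-Olshan subgroups. On placement it says: "These results will be reported in the statistical appendix as part of CSR". Protocol 10.2.8 specifies the same placement.

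**Dislodgements.** SAP 4.5.2 gives raw descriptive statistics by treatment (Table 14.2.6), a mean ± SE bar chart (Figure 14.2.4) and scatter plots against mass. The model in SAP 4.6 covers mass only.

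**The concern.** The crossover was chosen so that each subject serves as their own control, and the aim is a contrast with no adhesive. The displays a reader meets first treat the three conditions as if they were three separate groups. Their error bars contain the spread between subjects, most of which cancels from a treatment contrast if subjects differ consistently.

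The direction of the misreading matters. Protocol section 1 reports that the earlier study at this site could not show a difference between adhesive and no adhesive, and the present study asks whether the changed procedures correct that. Bars that are too wide for the comparison push a reader towards thinking that the method still does not separate the conditions. With no success criterion and no p-values, tables and charts carry the interpretation.

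For mass, the appendix of the same report holds the within-subject answer. For dislodgements nothing does: the reader has only raw means and bars for an outcome that Protocol 1.2.1 says will support the mass result.

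**Working it through.** There is no planned figure to reproduce: the readable text gives no SD, effect size or within-subject correlation, and SAP 1.4 says that no formal sample size calculation was made.

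**Inputs**
- n = 48 subjects (SAP 1.4: approximately 48, at most 50), complete data assumed.
- s = SD across subjects, assumed equal in the three conditions. Results are in units of s.
- r = correlation between a subject's results under two treatments. Not in the documents; assumed to be 0.3, 0.5 or 0.7. The rationale in Protocol 1.2.1 presumes that it is positive.
- The SE in Table 14.2.2.1 is taken as SD/√n. SAP 4.4.1.2 does not define it, but lists it with the raw mean and SD. The only SEs labelled within-subject are in the 16.1.9.x shells.

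**Formulas**
- SE of one bar: s/√48 = 0.144s.
- SE of a difference read from two bars as if independent: s√(2/48) = 0.204s, whatever r is.
- Within-subject SE of the same difference: s√(2(1−r)/48).
- Ratio of the two: 1/√(1−r).

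| r | SE from bars | Within-subject SE | Ratio | 0.35s in SEs, bars | 0.35s in SEs, within-subject |
|---|---|---|---|---|---|
| 0 | 0.204s | 0.204s | 1.00 | 1.71 | 1.71 |
| 0.3 | 0.204s | 0.171s | 1.20 | 1.71 | 2.05 |
| 0.5 | 0.204s | 0.144s | 1.41 | 1.71 | 2.42 |
| 0.7 | 0.204s | 0.112s | 1.83 | 1.71 | 3.13 |

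**How wide the affected range is.** The two readings fall on opposite sides of 1.96 SEs only for differences between 1.96 × the within-subject SE and 1.96 × 0.204s = 0.400s. That is 0.335s to 0.400s at r = 0.3, 0.283s to 0.400s at r = 0.5, and 0.219s to 0.400s at r = 0.7. Outside these ranges both readings point the same way. The 0.35s example lies inside all three.

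**Check by simulation.** A balanced six-sequence crossover with subject, period and treatment terms (4,000 runs per r) gave an SE from the bars of 0.204 throughout. The empirical SD of the difference was 0.172, 0.143 and 0.114 at r = 0.3, 0.5 and 0.7, and the average model SE was 0.170, 0.144 and 0.112.

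**Direction.** It does not need equal SDs. The variance of a difference is s₁² + s₂² − 2cov, and the bars leave out the covariance term, so any positive covariance makes them too wide for the comparison. The same holds for dislodgement counts, whose SD and r are also unknown.

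**Coverage of the outputs**
- Combined, maxillary, mandibular and subgroup mass: within-subject differences with 95% CIs are planned.
- Dislodgements: none in Protocol 10.2.7, Protocol 10.2.8, SAP 4.5.2 or SAP 4.6.

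**The case against.** The strongest reply is that the primary output was never meant as a contrast. The objectives tables ask to evaluate mass under each condition, Protocol 10.2.5 defines the primary analysis as descriptive statistics by treatment, and both documents say that there is no formal success criterion. SD/√n is a valid SE for a single treatment mean, so Table 14.2.2.1 would contain no wrong number. This stands.

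A reader might infer that the within-subject comparison of mass is missing. The documents do not support that: every mass in Figures 14.2.1 to 14.2.3 has a planned model-based difference with a 95% CI. A reader might also infer that Table 16.1.9.1.1 is misplaced and must move into section 14. Its placement follows Protocol 10.2.8, which presents these estimates as intended for future development work, and moving the table would change no result.

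The harm for mass is also conditional. It needs someone who compares the bars informally and ignores the CIs in the same report. It needs a positive r, which is not given, and it changes the reading only within the ranges shown above. The error is conservative. Dropout, which could leave the three raw columns describing different people, is at least visible, because the shell prints n and the number missing per treatment.

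None of this answers the dislodgement point. The endpoint is exploratory, which limits its weight, but no table elsewhere supplies the paired comparison.

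**Conclusion.** The point holds in two parts of unequal weight.

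For mass it is a fault of presentation. The raw SEs are correct for single means, and unsuited to comparing treatments by a factor of 1.20 to 1.83 over assumed correlations of 0.3 to 0.7. There is no discrepancy at zero correlation. The factor rests on 48 complete subjects, equal SDs and reading the undefined SE as SD/√n. The planned analysis of mass is sound and present.

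For dislodgements there is a real gap: the data are collected under all three conditions in the same subjects, are meant to support the mass findings, and have no planned within-subject contrast. Paired differences would use data already collected and, given positive correlation, compare the conditions more precisely than the raw columns do.

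The documents do not support saying that the primary analysis is wrong or that the trial would wrongly conclude that the method fails.

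**What to change.** 1. **Table 14.2.6:** add, for each adhesive pattern minus no adhesive, the paired difference in dislodgements: number of pairs, mean, SD, SE and 95% CI.
2. **Figure 14.2.4** (the dislodgement bar chart in SAP 4.5.2): base it on these differences with their 95% CIs.
3. **Table 14.2.2.1 and Figures 14.2.1 to 14.2.3:** repeat beside them the mixed-model mass differences and 95% CIs already planned in SAP 4.6. Leave the 16.1.9.x tables in the appendix.
4. **Footnote on the raw mean ± SE bars:** state that the SE is between-subject and not suited to comparing treatments.
5. **SAP section 5:** record these changes, since Protocol 10.2.5 and 10.2.7 describe raw summaries only and 10.2.8 assigns the model results to the appendix.

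The cost is SAP wording, edits to table and figure shells, and a small amount of programming for the paired dislodgement differences. No new data and no new model for mass are needed.

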4.4.1.3 Supportive Analyses

If there is more than 10% difference in the overall number of subjects between PP and ITT populations, a summary of the primary efficacy variable will be presented for all subjects in the PP population (Table 14.2.2.2).

4.4.2 Secondary Efficacy Variables

In this study secondary efficacy variables are not defined.

4.4.3 Handling of Missing Values/Censoring/Discontinuations

Missing data will not be replaced or imputed. Dropouts will be included in analyses up to the point of discontinuation.

4.5 Analysis of Exploratory Objectives

4.5.1 Exploratory Endpoints Definition

The exploratory endpoints defined in this study are as follows:

- Mass of peanuts under maxillary dentures.
- Mass of peanuts under mandibular dentures.
- Subject completed questionnaire.
- Mass of peanuts under combined maxillary and mandibular dentures in each subgroup (low and high Kapur-Olshan scores).
- The number of denture dislodgements reported by subjects during chewing.

4.5.2 Statistical Hypothesis, Model, and Method of Analysis

Descriptive statistics (number of subjects, number of missing data, raw means, SD, SE, minimum and maximum values) for the mass of peanuts recovered from mandibular and maxillary dentures will be provided by treatment group (Table 14.2.3).

For the subjects' response to questionnaires, descriptive statistics (number of subjects, number of missing data and percentages), mean score and SE of the response will be provided for each question by treatment group (Table 14.2.4).

Descriptive statistics (number of subjects, number of missing data, raw means, SD, SE, median, minimum and maximum values) for combined mass of peanuts recovered from mandibular and maxillary dentures will be provided by treatment group in low and high Kapur-Olshan groups of subjects (Table 14.2.5).

The number of denture dislodgements reported by subjects during chewing will be summarized descriptively (number of subjects, number of missing data, raw means, SD, SE, median, minimum and maximum values) by treatment group (Table 14.2.6). The bar chart to display mean (\pm SE) of number of denture dislodgements during chewing in each treatment group (Figure 14.2.4) will be presented.

Mass of peanuts will also be plotted against the number of dislodgements by all treatment groups in one plot (Figure 14.2.5.1) and by each treatment group in separate plots (Figures 14.2.5.2, 14.2.5.3, 14.2.5.4).

4.6 Additional Analysis

Adjusted means for mass of peanuts recovered from mandibular, maxillary (Table 16.1.9.2.1) and combined (Table 16.1.9.1.1) dentures, along with 95% confidence interval (CI) will also be reported by treatment group. These will be derived from a mixed model with period and treatment as fixed effects and subject as a random effect. The pair-wise comparisons will be performed and corresponding treatment differences, SE and 95% CI will be presented for all patients in ITT population. No p-value will be reported.

Using the same model as above, a subgroup analysis will be also conducted in low and high Kapur-Olshan groups of subjects. Adjusted means of combined masses of peanuts recovered from mandibular and maxillary denture, along with 95% CI will be presented by treatment groups for each sub-group (Table 16.1.9.3.1) for all patients in ITT population.

These results will be reported in the statistical appendix as part of CSR.

The assumptions underlying the mixed model will be examined using appropriate statistical method and if necessary, a suitable transformation of data or alternative non-parametric method based on ranks will be applied to obtain the inferential statistics. Hodges-Lehmann estimates of median of differences and Hodges-Lehmann 95% confidence intervals will be calculated.

